4.6. Safety Analyses

The following safety measures will be summarized and analyzed using the Safety Analysis Set. Patients will be analyzed according to the treatment to which they were assigned. Safety summaries will be presented by treatment arm as follows: LY3462817 300 mg, LY 3462817 700 mg, All LY3462817, and Placebo. (Coming from CPT Section 9.4.5. Other Safety Analysis and 9.4.6 Other Analyses), information on this section will be copied from protocol, if needed; it can be edited and additional details may be added.

4.6.1. Extent of Exposure

Duration of Exposure to Study Treatment

Duration of exposure on treatment (defined as time since first injection in days) during the Double-blind Treatment Period will be summarized by treatment arm and provided as listing. Duration of exposure on treatment will be calculated as:

(Date of last study visit during the Double-blind Treatment Period – Date of first injection + 1).

For patients who discontinue from the treatment, the date of discontinuation prior to Period 2 will be used.

Descriptive statistics for duration of exposure and the frequency and percentage of patients falling into the following ranges will be summarized: 0, >0, ≥ 7 days, ≥ 14 days, ≥ 30 days, ≥ 60 days, ≥ 84 days. The frequency and percentage of patients with duration of exposure in the following categories will also be summarized: 0 days, <14 days, ≥ 14 to <30 days, ≥ 30 to <60 days, ≥ 60 to <84 days, ≥ 84 days.

Overall exposure for each treatment arm will also be summarized in total patient years. This will be calculated as follows:

Exposure in patient years = Sum of duration of exposure (for all patients in treatment arm) / 365.25.

The analyses in Double-blind Treatment Period will be repeated for all visits in period 2 for subjects who remain on LY3462817 300 mg or LY3462817 700 mg.

Total Dose of Study Treatment

Total dose of active study treatment per subject will be summarized by active treatment arm using descriptive statistics. The total dose (mg) will be calculated as:

Total Dose = Sum over all injections received of [dose of LY (mg) prescribed per injection]

A by-patient listing of exposure duration and total dose will be provided.

4.6.2. Adverse Events

A treatment-emergent adverse event (TEAE) is defined as an event that first occurred or worsened in severity after baseline, with baseline defined as all pre-existing conditions recorded at Visit 1 and any AEs recorded before the first dose of study intervention (that is, during the interval between Visits 1 and 2 and recorded with the time of onset before the first dose of study intervention). The MedDRA Lowest Level Term (LLT) will be used in the treatment-emergent computation. The maximum severity for each LLT before the first injection will be used as baseline. Start date of adverse events will be compared with date of first injection and the date of Visit 10 (Week 24) to determine whether an adverse event is treatment-emergent. Should there be insufficient data for adverse event start date or severity to make this comparison; the adverse event will be considered treatment-emergent.

TEAEs will be coded according to established Medical Dictionary for Regulatory Activities (MedDRA) terms and summarized by MedDRA System Organ Class (SOC) and Preferred Term.

An overview of adverse events will summarize the percentage of patients experiencing deaths, SAEs, AEs reported as reason for discontinuation, TEAEs, and AEs possibly related to study treatment.

The frequency and percentage of patients with the following will be summarized using MedDRA Preferred Term nested within SOC.

- TEAEs
- TEAEs by maximum severity
- TEAEs related to study intervention
- TEAEs leading to study discontinuation
- SAEs including death
- SAEs by maximum severity
- SAEs related to study intervention
- Deaths
- AE of Special Interests (AESIs)

Events will be sorted alphabetically by SOC and then by decreasing total frequency within SOC. For incidence counts, each patient will be counted only once within each Preferred Term and within each SOC. Percentages will be based on the number of patients in a particular treatment arm. For events that are gender-specific, the denominator and computation of the percentage will include only patients from the given gender.

Adverse events of special interest will be identified by a standardized MedDRA query or a Lilly-defined MedDRA preferred term listing.

By-patient listings of all adverse events (including non-treatment-emergent events) recorded on the CRF, all TEAEs, TEAEs leading to study discontinuation, SAEs including death, and deaths during the Treatment Period will be presented by participant, visit, preferred term, treatment group, severity, and relationship to the treatment.

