Participant Disposition	
A detailed description of participant disposition will be provided, including a summary of the number and percentage of participants entered into the study and randomized, and number and percentage of participants who complete the study or discontinue, both overall and by reason for discontinuation. A summary of important protocol deviations will be provided.

Participant Characteristics	
Demographic data are collected and responded to demonstrate that the study population represents the target patient population. A summary of baseline participant characteristics, historical diagnoses, preexisting conditions, and prior therapies will be reported by treatment group using descriptive statistics. Other participant characteristics will be summarized by treatment group as deemed appropriate.

Concomitant Therapy	
Previous and concomitant medications will be summarized by treatment group and will be presented by Anatomical Therapeutic Chemical drug classes using the latest version of the WHO drug dictionary.

Treatment Compliance	No analyses are planned to assess treatment compliance, given that participants will receive study intervention directly from the investigator or designee at the study site, under medical supervision.
----------------------	--

Summary statistics for continuous measures will include sample size, mean, standard deviation, median, minimum, and maximum.

For categorical data, summary statistics will include sample size, frequency, and percentages. Percentages will be rounded to one decimal place. Unless otherwise specified, Fisher's exact test will be used for making treatment comparisons.

All statistical tests of treatment effects will be performed at two-sided significance levels of 0.05 and 0.10, respectively, unless otherwise specified. All p-values will be presented to three decimal places.

The Treatment Period is defined as the combination of Period 1 with double-blind treatment and Period 2.

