The baseline period is defined as Visit 1 through pre-dose Visit 2. The Double-blind Treatment Period starts after the first injection of study treatment at Visit 2 (Week 0) and ends on the date of Visit 6 (Week 12) or the early discontinuation visit. The Period 2 starts after the date of Visit 6 (Week 12) or the early discontinuation visit and lasts up to 24 weeks following the last injection of study treatment. Additional follow-up beyond 24 weeks may be deemed necessary and, if so, any data collected will be considered as part of Period 2.

Unless otherwise specified, baseline for the Treatment Period is defined as the last non-missing assessment on or prior to the date of the first injection of study treatment, scheduled to be given at the end of Visit 2. Any assessment collected after the first injection through the date of the Week 12 or early discontinuation visit is defined as post-baseline for the Treatment Period.

Data collected at early discontinuation visits will be mapped to the next planned visit number for that patient. For by-visit summaries, only visits in which a measure was scheduled to be collected will be summarized.

Summaries of safety data collected during Period 2 will be presented separately. Unless otherwise specified, follow-up baseline is defined as the last non-missing assessment on or prior to the date of Week 12 or the date of the early discontinuation visit.

Change from baseline will be calculated as the post-baseline value minus the baseline value. Percent change from baseline is defined as $(100 \times (\text{post-baseline} - \text{baseline}) / \text{baseline})$. If all baseline values are missing for a particular variable, the change from baseline and percent change from baseline will not be calculated.

The statistical analyses of efficacy, health outcomes, and safety measures will be performed using SAS Version 9.4 or higher. Lilly will be responsible for conducting analyses.

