4.6.2.1. Hypersensitivities

Hypersensitivities will be defined using the following terms:

- Anaphylactic reaction standardized MedDRA query (SMQ) excluding the Preferred Term Anaphylactic transfusion reaction
- Angioedema SMQ excluding the Preferred Terms Oedema neonatal and Peripheral oedema neonatal
- Severe cutaneous adverse reactions SMQ Narrow Search terms and the following Broad Search terms:
 - Drug eruption
 - Drug rash with eosinophilia and systemic symptoms
 - Lip exfoliation
 - Mucosal exfoliation
 - Penile exfoliation
 - Skin exfoliation

- Stomatitis
 - Tongue exfoliation
 - Vaginal exfoliation
- Additional Preferred Terms including:
 - Asphyxia
 - Dermatitis
 - Dermatitis allergic
 - Dermatitis atopic
 - Dermatitis contact
 - Diastolic hypotension
 - Eczema
 - Eosinophilic oesophagitis
 - Erythema nodosum
 - Hypotension
 - Immediate post-injection reaction
 - Injection related reaction
 - Orthostatic hypotension
 - Photosensitivity allergic reactions
 - Photosensitivity reaction
 - Presyncope
 - Rash vesicular
 - Reaction to drug excipients
 - Red man syndrome
 - Serum sickness
 - Serum sickness-like reaction
 - Syncope
 - Type II hypersensitivity
 - Type III immune-complex-mediated reaction
 - Type IV hypersensitivity reaction
 - Toxic skin eruption
 - Urticaria contact
 - Urticaria vesiculosa

The frequency and percentage of patients experiencing treatment-emergent hypersensitivities will be summarized by treatment arm, maximum severity, SOC, and Preferred Term during Treatment Period. The frequency and percentage of patients experiencing treatment-emergent hypersensitivities will also be summarized by treatment arm and timing category (immediate, acute reaction, delayed reaction or reaction after more than 15 days).

Exposure-adjusted incidence rates (per 100 patient years) of treatment-emergent hypersensitivities within the following time intervals will be calculated as detailed below.

- ≥ 0 to ≤ 6 weeks since the date of first injection:

Interval start date = Date of first injection,

Interval end date = Date of first injection + 42 days.

- > 6 to ≤ 12 weeks since the date of first injection:
Interval start date = Date of first injection + 43 days,
Interval end date = Date of first injection+ 84 days.
- ≥ 24 weeks since the date of first injection:
Interval start date = Date of first injection + 85,
No Interval end date, Treatment Period planned for 24 weeks

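### SAP safety count tables run by arm to Week 24 although SAP 4.1 also separates Period 2, so nominally 10 of 24 placebo-column weeks are standard of care; SAP 4.6 also groups as assigned, not as received

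*SAP*

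**What the plan says.** **Text that carries the window to Week 24.** SAP 4.1: "The Treatment Period is defined as the combination of Period 1 with double-blind treatment and Period 2". SAP 4.6.2, on whether an event is treatment-emergent: "Start date of adverse events will be compared with date of first injection and the date of Visit 10 (Week 24". SAP 4.6.2.1 then has "hypersensitivities will be summarized by treatment arm, maximum severity, SOC, and Preferred Term during Treatment Period". Sections 4.6.2.2 to 4.6.2.5 (infusion site reactions, infections, malignancies, depression) are also by arm over the Treatment Period.

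**Text that stops at Week 12 or splits the periods.** In SAP 4.1 the Double-blind Treatment Period "ends on the date of Visit 6 (Week 12) or the early discontinuation visit". An assessment after the first injection and "through the date of the Week 12 or early discontinuation visit is defined as post-baseline for the Treatment Period". The same section adds: "Summaries of safety data collected during Period 2 will be presented separately". It gives Period 2 a further end of its own: it "lasts up to 24 weeks following the last injection of study treatment".

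**Treatment after Week 14.** Protocol 4.1 and 6.5.3 stop study infusions for all placebo participants and for LY3462817 participants not in low disease activity. These participants should then receive standard of care at the investigator's discretion. SAP 1.2 instead has everyone on LY3462817 in Period 2.

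**Grouping.** SAP 4.6 groups safety by assigned treatment. SAP 3 groups it by treatment actually received, and protocol 9.3 by treatment actually received within each period.

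**The concern.** Describing safety and tolerability compared with placebo is a secondary objective (protocol 3). A column headed Placebo that runs to Week 24 would count events arising on investigator-chosen standard of care as placebo events. The LY3462817 columns would likewise count events in participants who had stopped the drug.

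The SAP can also be programmed in two ways. The main list of adverse event tables in SAP 4.6.2 (TEAEs, SAEs and so on) states no reporting window. A programmer who follows the Treatment Period definition would build different TEAE and SAE tables from one who follows the Week 12 cut and the separate Period 2 summaries.

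The grouping conflict is a separate matter. It would change a table only if someone received a treatment other than the one assigned, and it does not produce the 10 of 24 weeks.

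**Working it through.** **1. The plan's own length.** Protocol 4.1 gives Periods 1 and 2 as 12 weeks each: 12 + 12 = 24. In the Schedule of Activities Week 24 is Day 168, and 168/7 = 24. SAP 4.6.2.1 also plans the Treatment Period at 24 weeks. The figure reproduces.

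**2. Placebo column pooled to Week 24.** Inputs are Week 14 = Day 98 ± 7 and Week 24 = Day 168 ± 7. Share after the planned switch = (end day − switch day)/end day.
- Nominal: (168 − 98)/168 = 70/168 = 41.7%, or 10 of 24 weeks.
- Smallest with visit windows: (161 − 105)/161 = 56/161 = 34.8%.
- Largest: (175 − 91)/175 = 84/175 = 48.0%.

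For 20 placebo participants with full follow-up, the pooled window holds 20 × 168/365.25 = 9.2 patient-years, of which 20 × 70/365.25 = 3.8 fall after Week 14. Period 1 alone holds 20 × 84/365.25 = 4.6, none of it after Week 14.

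**3. LY3462817 columns.** Let p be the share in low disease activity at Week 14. The documents do not give p, so the values below are assumptions, and later switches among continuers are ignored. LY share = (70/168) × (1 − p). Gap to placebo = (70/168) × p.
- p = 10%: 37.5%, gap 4.2 points.
- p = 30%: 29.2%, gap 12.5 points.
- p = 50%: 20.8%, gap 20.8 points.

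**4. Direction.** If events occur on standard of care at r times the placebo rate (r assumed), the pooled placebo-arm rate is (14 + 10r)/24 times the placebo rate. For r = 0.5 this is 19/24 = 0.79; for r = 2 it is 34/24 = 1.42. The documents give no r, so the sign is open.

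**5. Last hypersensitivity interval.** SAP 4.6.2.1 labels it "≥ 24 weeks since the date of first injection", but its start date is first injection plus 85 days and it has no end date. Taken to Week 24, 70 of its 84 days (83%) in the placebo arm fall after Week 14. The SAP does not say whether person-time stops at the switch. The only Period 2 exposure summary (SAP 4.6.1) covers participants who stay on LY3462817.

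**6. What is not affected.** The hypersensitivity rates for 0 to 6 and over 6 to 12 weeks, the 12-week Kaplan-Meier estimate for infections, and double-blind exposure all end by Week 12.

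**7. Scale.** One participant is 1/20 = 5 percentage points in an arm of 20 and 1/40 = 2.5 points in the arm of 40. This shows how coarse the tables are; it does not estimate bias.

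**The case against.** - **Protocol 9.3 might be read as demanding by-period adverse event tables.** It does not. It is a population definition that says under which treatment a participant is grouped in each period. Protocol 9.4.7 summarises adverse events by treatment group and mentions treatment period only for exposure. What stands is narrower: a single placebo column to Week 24 does not fit the protocol 9.3 grouping rule. The conflict over tables lies mainly inside the SAP.
- **SAP 4.1 could be met by adding Period 2 tables to the pooled ones.** True, and the window name appears twice in one sentence in both SAP 4.6.2.2 and 4.6.2.3, which hints that two windows were meant. But the AESI sections specify no Period 2 table, and adding one would leave the pooled columns mixed.
- **Several displays already separate the first 12 weeks.** Correct. The defect is in the count and percentage tables and in the interval after day 84, not in every AESI display.
- **A reader might take 42% as the distortion of the comparison.** It is a share of calendar time in one arm. The LY3462817 arms also switch, and the affected tables count participants, not weeks.
- **A reader might infer a longer contaminated window from the extended end of Period 2, or active drug in the placebo column from SAP 1.2.** SAP 4.6.2 stops treatment-emergent status at Visit 10, so the first does not reach these tables. The second contradicts protocol 4.1 and 6.5.3. The SAP is based on a protocol dated 05AUG2020, while the protocol supplied cites a decision of 08 September 2020, so version lag is a plausible cause. The passages must be reconciled.
- **Safety is descriptive, and events are listed by participant and visit.** Agreed. The effect is on interpretation, not on a formal test.

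**Conclusion.** Wrong as written and worth correcting, within descriptive safety output. Read literally, the SAP gives AESI and depression counts and percentages by arm to Week 24, while its own general section stops post-baseline at Week 12 and separates Period 2. The pooled placebo column then nominally holds 42% standard of care (35% to 48% with visit windows). This assumes full follow-up and a switch at the Week 14 visit, which the protocol words as a recommendation at the investigator's discretion. The LY3462817 columns hold a smaller share that depends on a low-disease-activity rate the documents do not state. Neither the size nor the direction of any between-arm bias can be derived.

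The grouping conflict in SAP 4.6 is a plain contradiction of SAP 3 and protocol 9.3, with no size that can be computed in advance. The primary efficacy analysis is untouched.

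**What to change.** 1. In SAP 4.1 and 4.6, state that between-arm safety tables (TEAE, SAE, AESI) use Period 1 as the SAP already defines it, grouped by treatment received. Delete the as-assigned sentence in SAP 4.6, and give each table listed in SAP 4.6.2 a reporting window.
2. Present Period 2 and follow-up separately as three sets: LY3462817 continuers by dose, LY3462817 to standard of care, and placebo to standard of care. Give each its own person-time. Keep any pooled 24-week table only as supplementary, labelled as including standard of care.
3. Correct the label of the last interval in SAP 4.6.2.1 and give the interval an end. Settle when Period 2 ends in SAP 4.1, and reconcile SAP 1.2 and 4.1 with protocol 4.1 and 6.5.3.

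The cost is SAP wording and one extra set of tables, with no new data. The downside is real: the fourth infusion is given at Visit 6, where Period 1 ends. Events that follow it, including those in Weeks 12 to 14 before any planned switch, would appear only in the Period 2 and supplementary tables.

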Administer study drug		X		X	X	X		X	X	X				During Weeks 16 - 24 administer study drug only if participant achieved low disease activity at Week 14.

Abbreviations: AESI = adverse event of special interest; anti-HBc = hepatitis B core antibody; BP = blood pressure; C-SSRS = Columbia-Suicide Severity Rating Scale; ECG = electrocardiogram; ED = early discontinuation visit; ET = early termination; ETV = early termination visit; HBcAb+ = hepatitis B core antibody positive; HBsAg = hepatitis B surface antigen; ICF = informed consent form; IgA = immunoglobulin A; IgG = immunoglobulin G; IgM = immunoglobulin M; MRI = magnetic resonance imaging; PD-1 = programmed cell death protein 1; PD-L1 = programmed cell death ligand 1; PPD = purified protein derivative; PR = pulse rate; RA = rheumatoid arthritis; T = temperature; TBNK = T cells, B cells, natural killer cells; V = visit; VAS = visual analog scale.

2. Introduction

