4.1. Overall Design

This is a Phase 2, proof-of-concept, placebo-controlled, double-blind, randomized study in adult participants with moderately to severely active RA who have had an inadequate response to csDMARDs, or to bDMARDs/tsDMARDs. Participants will be administered LY3462817 or placebo IV Q4W.

Screening Period (Visit 1, Days -42 to -1)

Participants will sign the informed consent document(s) at Visit 1, prior to completion of any procedures. Participants will be evaluated for study eligibility \leq 42 days prior to the baseline visit (Visit 2).

Period 1: Double-blind Treatment (Visits 2 to 6; 12 weeks)

At the baseline visit (Visit 2), participants who fulfill the eligibility criteria will be randomized to receive LY3462817 700 mg, LY3462817 300 mg, or placebo in an allocation ratio of 2:1:1.

The double-blind treatment period will establish the clinical efficacy and safety of LY3462817. The study will be evaluated for the primary objective at the end of the double-blind treatment period.

Period 2 (Visits 6 to 10; 12 weeks)

Data from a Study KDAC interim analysis that includes Week 12 data from participants in the KDAC 700-mg cohort, must be reviewed prior to a participant proceeding to Period 2 in Study KDAD.

At Week 14, participants will be evaluated for clinical benefit.

Participants assigned to LY3462817 at baseline, and achieving low disease activity (CDAI \leq 10) at Week 14 will continue to receive LY3462817 at the randomized dose through Week 24 to assess safety and tolerability and evaluate efficacy.

All other participants at Week 14, regardless of baseline treatment assignment, will stop study drug infusions and should receive standard of care treatment at the investigator's discretion.

Posttreatment Safety Follow-up Period (Visits V801 and 802; 12 weeks)

Following Period 2, participants will be followed posttreatment for 12 weeks to assess safety, study drug exposure, and clinical disease activity measures. Participants who discontinue the study intervention per Section 7 will have their last visit at 12 weeks from the last administration of the study intervention.

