9.4.7. Other Safety Analyses

Analyses/measures	Presented...
Safety analyses: AEs, SAEs, C-SSRS, vital signs, ECGs, and laboratory analytes	Descriptively summarized by treatment group, will use the safety population data
Categorical safety measures	Summarized with counts by visit
Continuous safety measures	Summarized as mean change by visit
Exposure to study intervention	Calculated for each participant and summarized by treatment group by treatment period

Adverse events

Adverse events will be coded according to the Medical Dictionary for Regulatory Activities (MedDRA) and summarized by system organ class, preferred term, severity, and relationship to the study intervention. All AEs, including pre-existing conditions, will be listed by participant, visit, preferred term, treatment group, severity, and relationship to the treatment.

Treatment-emergent adverse events

A TEAE is defined as an event that first occurred or worsened in severity after baseline, with baseline defined as all pre-existing conditions recorded at Visit 1 and any AEs recorded before the first dose of study intervention (that is, during the interval between Visits 1 and 2 and recorded with the time of onset before the first dose of study intervention). For events that are gender specific, the denominator and computation of the percentage will include only participants from the given gender.

The number and percentage of participants who experienced TEAEs, TEAEs by maximum severity, deaths, SAEs, TEAEs related to study intervention, discontinuations from the treatment due to an AE, and AESIs will be summarized. Treatment-emergent adverse events (all, by maximum severity), SAEs including deaths, and AEs that lead to treatment discontinuation will be summarized and analyzed by MedDRA system organ class and preferred term.

Treatment-related TEAEs (TEAEs related to study intervention) are defined as events that are indicated by the investigator on the eCRF to be related to treatment.

Adverse events of special interest will be identified by a standardized MedDRA query or a Lilly-defined MedDRA preferred term listing.

Suicide-related thoughts and behaviors

Suicide-related thoughts and behaviors occurring during treatment will be summarized based on responses to the C-SSRS consistent with the C-SSRS Scoring and Data Analysis Guide (Columbia Lighthouse Project WWW).

Follow-up emergent adverse events

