Follow-up emergent AEs, SAEs including deaths, and AEs that lead to study discontinuation will be summarized.

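### SAP 4.6.2 closes the treatment-emergent window at Visit 10, when a Week 24 infusion is still scheduled, and specifies none of the follow-up-emergent AE tables that protocol 9.4.7 plans

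*SAP*

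**What the plan says.** **Treatment-emergent window.** Protocol 9.4.7 sets a starting point and no end: "A TEAE is defined as an event that first occurred or worsened in severity after baseline". SAP 4.6.2 repeats that definition and adds an end: "Start date of adverse events will be compared with date of first injection and the date of Visit 10 (Week 24".

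**Follow-up events.** Protocol 9.4.7 also commits to a second set of tables: "Follow-up emergent AEs, SAEs including deaths, and AEs that lead to study discontinuation will be summarized". The list of AE tables in SAP 4.6.2 has no follow-up-emergent item. SAP 1 and SAP 4.9 both say that nothing has changed from the protocol's analyses.

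**Dosing at Visit 10.** Under protocol 4.1, LY3462817 participants with low disease activity at Week 14 "will continue to receive LY3462817 at the randomized dose through Week 24"; all others "will stop study drug infusions and should receive standard of care treatment". The Schedule of Activities marks study drug at Visits 8, 9 and 10, with the comment "During Weeks 16 - 24 administer study drug only if participant achieved low disease activity at Week 14".

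**Follow-up.** Protocol 4.1: "Following Period 2, participants will be followed posttreatment for 12 weeks to assess safety, study drug exposure, and clinical disease activity measures". Protocol 8.3.1 collects all AEs until participation ends.

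**A second end date in the SAP.** SAP 4.1 says that Period 2 "lasts up to 24 weeks following the last injection of study treatment", and it makes Period 2 part of the Treatment Period. It promises separate summaries of Period 2 safety data, and sets the follow-up baseline at Week 12 or early discontinuation.

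**The concern.** A treatment-emergent window that ends with the treatment period is normal practice when follow-up-emergent tables take over from there. The SAP keeps the cut-off and does not specify those tables. Because the cut-off falls on a dosing day, the time left out includes the time when a final infusion is most likely to act. Protocol 2.2 gives a terminal half-life of about 10 days. Protocol 4.3 says that 350 mg and 700 mg saturate the receptor in plasma for 4 weeks or more.

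The rule is also lopsided. A participant whose last infusion is at Week 12 has 12 post-dose weeks counted as treatment-emergent, most of them after the move to standard of care. A participant dosed through Week 24, the longest-exposed group, has none.

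Safety and tolerability is a secondary objective. With two end dates in the SAP, two programmers could build different treatment-emergent tables from the same text.

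**Working it through.** **Inputs.** Nominal days from the Schedule of Activities: Visit 6 (Week 12) Day 84, Visit 8 (Week 16) Day 112, Visit 9 (Week 20) Day 140, Visit 10 (Week 24) Day 168, Visit 802 Day 252. Half-life 10 days (protocol 2.2). About 40 + 20 = 60 LY3462817 participants of about 80 (protocol 9.2).

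**1. The plan's own figure.** Visit 802 minus Visit 10 = 252 − 168 = 84 days = 12 weeks, as protocol 4.1 states.

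**2. Coverage of the 84 days after the last infusion.** Days inside the SAP 4.6.2 window = min(84, 168 − day of last infusion).

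| Last infusion | Calculation | Days inside | Days outside |
|---|---|---|---|
| Week 12 | min(84, 168 − 84) | 84 | 0 |
| Week 16 | min(84, 168 − 112) | 56 | 28 |
| Week 20 | min(84, 168 − 140) | 28 | 56 |
| Week 24 | min(84, 168 − 168) | 0 | 84 |

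The Week 16 and Week 20 rows use the nominal Day 168. SAP 4.6.2 does not say which date replaces Visit 10 for someone who never attends it.

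**3. Drug remaining after the last infusion.** Fraction = 0.5^(days/10). At 28 days, 0.5^2.8 = 0.14; at 50 days, 0.5^5 = 0.03; at 84 days, 0.5^8.4 = 0.003. The first weeks of follow-up are still exposed time.

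**4. The competing end date in SAP 4.1.** The limit of 24 weeks is 168 days. After a Week 24 infusion, Period 2 could run to 168 + 168 = Day 336 (Week 48), past Visit 802. After a Week 12 infusion it could run to 84 + 168 = Day 252, the day of Visit 802. So the SAP 4.1 period takes in the whole follow-up, while SAP 4.6.2 stops at Day 168. Other sections do not settle it:
- SAP 4.6.2.1 describes a 24-week Treatment Period but leaves its last interval open-ended.
- SAP 4.6.2.3 names a separate post-treatment follow-up period.
- SAP 4.6.2.6 stops counting at Visit 10 or early discontinuation.

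**5. Which outputs lose events that start after the Week 24 infusion date.**
- Lost: the treatment-emergent AE tables in SAP 4.6.2, and the registry table of non-serious events (SAP 6.3), which requires an event to be treatment-emergent.
- Thinned if the Visit 10 rule governs: the treatment-emergent breakdowns for hypersensitivity, infusion site reactions, infections and malignancies (SAP 4.6.2.1 to 4.6.2.4). The hypersensitivity timing table has a class for reactions later than 15 days, which an event following the Week 24 infusion could not enter.
- Kept: the SAE, death and special-interest tables in SAP 4.6.2, which state no treatment-emergent limit; the registry SAE table, which includes SAEs whether or not they are treatment-emergent; and the listing of all AEs. Events whose start date or severity is too incomplete to compare default to treatment-emergent.

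**6. Number affected.** The documents give no rate of low disease activity at Week 14. Assuming that 10% to 40% of LY3462817 participants continue through Week 24: 0.10 × 60 = 6 and 0.40 × 60 = 24. The ceiling is 60.

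**The case against.** The strongest reply is that little is hidden. Hypersensitivity, infusion site reactions, infections and malignancy are all events of special interest (protocol 8.3.6) with a planned table that has no treatment-emergent limit. SAEs and deaths are tabulated too. SAP 4.1 promises separate Period 2 safety summaries over a period long enough to cover follow-up. And since SAP 4.9 declares no change, the protocol's commitment arguably still stands and the SAP has merely not spelled it out.

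Much of this is right, and it rules out three stronger readings that a reader might infer:
- **That everyone loses the 12 weeks after the final dose.** Under the protocol, placebo participants and LY3462817 participants without low disease activity have their last scheduled infusion at Week 12. All 84 of their post-dose days are inside the window.
- **That late events would appear only in listings.** The SAE, death and special-interest tables can carry them.
- **That the SAP has nothing at all for follow-up.** SAP 4.1 has the general promise.

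The reply does not dispose of the point. The promise in SAP 4.1 names no AE table, and its follow-up baseline is Week 12, not the end of Period 2 dosing. Its period also contradicts SAP 4.6.2. An analysis that survives only by the SAP's silence has no definition, baseline or window to program from.

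The SAP says that it is based on a protocol dated 05AUG2020, while the supplied protocol contains September 2020 data. SAP 1.2 has all subjects receiving LY3462817 in Period 2, which also disagrees with the supplied protocol and must be reconciled. A version difference may explain the mismatch but does not remove it.

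**Conclusion.** The point holds in a limited form. The SAP specifies no follow-up-emergent AE table although the protocol plans one, and its treatment-emergent cut-off coincides with a scheduled infusion and contradicts its own period definitions. The loss is complete (0 of 84 days covered) only for LY3462817 participants dosed at Week 24. It is partial after a last infusion at Week 16 or 20, and nil after Week 12.

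What is certainly missing from the treatment-emergent tables is datable, non-serious events outside the special-interest categories that start after the Week 24 infusion date. The special-interest breakdowns lose late events if the Visit 10 rule governs. The planned follow-up-emergent summary is unspecified for everyone followed past Week 24.

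This rests on nominal visit days, on the dosing pattern in the supplied protocol, and, for the range of 6 to 24 participants, on an assumed continuation rate of 10% to 40%. No data are lost, because AEs are collected to the end of participation, and the primary endpoint is untouched. It should be corrected before unblinding.

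**What to change.** 1. Add follow-up-emergent tables to SAP 4.6.2 for AEs, for SAEs including deaths, and for AEs leading to study discontinuation, as protocol 9.4.7 plans. Use each participant's last treatment-period visit as baseline and run to the last follow-up visit.
2. In SAP 4.1, define Period 2 as Week 12 to Week 24, with a separate 12-week post-treatment follow-up. Make the Treatment Period, the follow-up baseline and the window in SAP 4.6.2 agree with it, and state the end date for participants who have no Visit 10.
3. Do not extend the treatment-emergent window to the last visit for all participants. Someone last infused at Week 12 and followed to Visit 802 would then have events up to 252 − 84 = 168 days (24 weeks) after the last dose counted as treatment-emergent, mostly while on standard of care.

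The cost is SAP wording and one set of tables. No new data are needed.
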